## LIST OF ABBREVIATIONS AND DEFINITIONS OF TERMS

LIST OF ADDREVIAT	I IONS AND DEFINITIONS OF TERMS	
Abbreviation	Expanded Term	
ADaM IG	Analysis Data Model Implementation Guide	
AE	Adverse Event	
AESI	Adverse Event of Special Interest	
Ae%	Amount of drug eliminated in urine	
ALT	Alanine Aminotransferase	
AST	Aspartate Aminotransferase	
ATC	Anatomical Therapeutic Chemical	
AUC	Area under the plasma concentration-curve	
CL	Total clearance	
C max	Maximum plasma concentration	
CDISC	Clinical Data Interchange Standards Consortium	
CSR	Clinical Study Report	
DMC	Data Monitoring Committee	
DMD	Duchenne Muscular Dystrophy	
eCRF	Electronic Case Report Form	
ECG	Electrocardiogram	
ECHO	Echocardiogram/Echocardiography	
GCP	Good Clinical Practices	
ICH	International Conference on Harmonisation	
IEC	Independent Ethics Committee	
IRB	Institutional Review Board	
IV	Intravenous	
IVAD	Implantable Venous Access Device	
KIM-1	Kidney Injury Moledule-1	
MedDRA	Medical Dictionary for Regulatory Activities	

Protocol 4658-102	Statistical Analysis Plan for Final Analysis
РК	Pharmacokinetics
РТ	Preferred Term
SAE	Serious Adverse Event
SAP	Statistical Analysis Plan
SD	Standard Deviation
SDTM IG	Study Data Tabulation Model Implementation Guide
SMQ	Standard MedDRA Query
SOC	System Organ Class
t½	Elimination half-life
TEAE	Treatment Emergent Adverse Event
Tmax	Time to maximum plasma concentration
$V_{ss}$	Apparent volume of distribution at steady state
WHO Drug	World Health Organization Drug Dictionary

## **1. INTRODUCTION**

The purpose of this statistical analysis plan (SAP) is to provide a detailed description of the statistical methods and procedures that will be used to analyze and report results for Study 4658-102, entitled "An Open-Label Safety, Tolerability, and Pharmacokinetics Study of Eteplirsen in Young Patients with Duchenne Muscular Dystrophy Amenable to Exon 51 Skipping"

This SAP has been prepared based on Protocol Version 4, dated 07 February 2020 for Study 4658-102,

## 2. STUDY OBJECTIVES

#### Study 4658-102

Primary Objective:

The primary objective of Study 4658-102 is to evaluate the safety and tolerability of eteplirsen administered once weekly by intravenous (IV) infusion in male Duchenne muscular dystrophy (DMD) patients ages 6 months to 48 months, inclusive.

Secondary Objective:

The secondary objective of Study 4658-102 is to determine the pharmacokinetics (PK) of eteplirsen at the 2, 10, 20, and 30-mg/kg dose levels administered once weekly by IV infusion in male DMD patients ages 6 months to 48 months, inclusive.

## **3. STUDY ENDPOINTS AND OTHER VARIABLES**

The study endpoints for which the statistical methods will be described in this SAP comprise of safety, PK, and efficacy endpoints.

#### Study 4658-102

[figure not shown]
The primary endpoint is safety and tolerability of eteplirsen in the study population, as measured by:

- Incidence of adverse events (AEs)
- Abnormal changes from Baseline or clinically significant worsening of clinical safety laboratory abnormalities (hematology, chemistry, coagulation, urinalysis)
- Abnormal changes from Baseline or worsening of vital signs
- Abnormal changes from Baseline or worsening of physical examination findings
- Abnormal changes from Baseline or clinically significant worsening of electrocardiograms (ECGs)
- Abnormal changes from Baseline or clinically significant worsening of echocardiograms (ECHOs).

The secondary endpoint is to determine the PK of eteplirsen by population PK methods, including assessment of the following PK parameters if evaluable:

- Maximum plasma concentration (Cmax)
- Time of  $C_{max}(T_{max})$
- Area under the plasma concentration-curve (AUC)
- Apparent volume of distribution at steady state (Vss)
- Elimination half-life (t1/2)
- Clearance (CL)
- Amount of drug eliminated in urine (Ae%).

## **4. STUDY DESCRIPTION**

## 4.1. Study Overview

#### Study 4658-102

This is a multicenter, open-label, dose-escalation study to evaluate the safety, tolerability, PK, and efficacy of once-weekly IV infusions of eteplirsen in approximately 12 male patients, ages 6 months to 48 months (inclusive), who have genotypically confirmed DMD with a deletion mutation amenable to exon 51 skipping.

Patients will be evaluated for inclusion during the Screening Period of up to 2 weeks to assess eligibility. Written informed consent from the parent/legal guardian to participate in the study must be obtained prior to beginning any study-related procedures.

Patients will be enrolled into 1 of 2 age cohorts: Cohort 1 of approximately 6 male patients age 24 to 48 months and Cohort 2 of approximately 6 male patients age 6 months to <24 months.

After the first 3 patients in Cohort 1 have completed 12 weeks of eteplirsen therapy, including 2 infusions each at 2, 4, 10 and 20 mg/kg and 4 infusions at 30 mg/kg, the Data Monitoring Committee (DMC) will review the safety data and determine whether to begin enrollment of the younger patients (Cohort 2). The DMC will also review safety data at least weekly through the first 12 weeks of dosing for the first 3 patients of each age cohort. Reviews will be at least quarterly thereafter.

The dose-titration period will last 10 weeks overall (1 infusion/week) to slowly achieve the target dose of 30 mg/kg. Eteplirsen dosing will begin at 2 mg/kg for 2 weeks (Weeks 1 and 2) and will escalate to 4 mg/kg (Weeks 3 and 4), 10 mg/kg (Weeks 5 and 6), 20 mg/kg (Weeks 7 and 8), and 30 mg/kg (Weeks 9 and 10). Patients will continue to receive 30 mg/kg eteplirsen for the duration of the study. The duration of each patient's treatment in the study is expected to be at least 48 weeks (including the 10-week titration period), and patients may continue to receive treatment in the study for up to 96 weeks. Study drug may be interrupted or discontinued for specific safety reasons.

Safety will be regularly assessed throughout the study via the collection of AEs, clinical safety laboratory test results (blood chemistry, hematology, coagulation, urinalysis), ECGs, ECHOs, vital signs, and physical examinations.

Plasma and urine samples for PK assessments will be collected at Week 2 (2 mg/kg dose level), Week 6 (1 -mg/kg dose level), Week 8 (20 mg/kg dose level) and at Weeks 10 and 24 (3 -mg/kg dose level). Serial PK samples will be collected pre-dose, immediately prior to the end of infusion (prior to flush), and approximately 1 to 3 hours and 6 to 8 hours after completion of study drug infusion. Urine PK samples will be collected over the first 4 hours after start of infusion.

Statistical Analysis Plan for Final Analysis

Approximately 4 weeks after the last eteplirsen infusion (regardless of the duration of the patient's participation in the study), patients will be required to return to the study site for safety evaluations. The total duration of patient participation, including Screening, Titration/Treatment, and Safety Follow-up periods is up to 101 weeks.

## 4.3. Randomization and Blinding

Both 4658-102 are open-label single arm studies and, therefore, all patients will receive eteplirsen.

## 4.4. Planned Analyses

## 4.4.1 Safety Review

The DMC will be comprised of a group of individuals with pertinent methodological and clinical expertise relevant to the study design and background population, to review the conduct of the study and the emerging safety, PK, and efficacy data on an ongoing basis

Statistical Analysis Plan for Final Analysis

in order to ensure that clinical trial participants are not exposed to unreasonable or unnecessary risks. The DMC will advise the study team and study investigators on safety aspects of dose interruption/continuation and dose escalation for the study. The DMC will begin their duty before the start of the clinical trial and will continue for the entire duration of the study.

The activities and composition of this committee are outlined in the DMC Charter which was ratified during the initial DMC meeting, prior to the commencement of dosing of the study patients, on 24 June 2019. The reviews will be performed at least weekly through the first 12 weeks of dosing for the first 3 patients of each age cohort and at least quarterly thereafter. Oversight and monitoring of the clinical study by the DMC will be performed in compliance with International Conference on Harmonisation (ICH) Good Clinical Practice (GCP) guidelines. These safety monitoring functions are distinct from the requirements for study review and approval by an Institutional Review Board (IRB) or Independent Ethics Committee (IEC).

#### 4.4.2 Final Analysis

Study 4658-102 final analysis of safety and efficacy will be conducted once the last patient completes the efficacy visit and the resulting database including AEs and concomitant medications is cleaned, quality assured, and locked through the data cut.

All statistical analyses

will be performed by or under the supervision of the Sponsor.

All available data will be included in data listings and tabulations.

## 4.5. Analysis Set

The Safety set includes all patients who are enrolled in Study 4658-102 and receive at least 1 dose of eteplirsen while in Study 4658-102. This analysis set will be used for analyses of all endpoints for the 4658-102 Final Analysis, unless stated otherwise.

## 5. GENERAL STATISTICAL METHODS AND CONVENTIONS

## 5.1. General Methods

Summary statistics will be presented by cohort, unless stated otherwise.

For continuous variables, descriptive statistics will include the number of patients with data to be summarized (n), mean, standard deviation (SD), median, minimum, and maximum.

For categorical/qualitative variables, descriptive statistics will include frequency counts and percentages. The total number of patients in the cohort will be used as the denominator for percentage calculations, unless stated otherwise.

Summaries will be for the following cohorts:

- Cohort 1 (age 24 to 48 months)
- Cohort 2 (age 6 to <24 months)

safety s	et for the final analysis of 4658-1	102.	All analyses will be displayed on the
5.2.	Handling of Missing Data	a	
5.2.1			

## 5.2.5 Imputation of Missing Laboratory Values

Laboratory data that are continuous in nature, but are less than the lower limit of quantitation or above the upper limit of quantitation will be imputed to the value of the lower or upper limit plus or minus 2 significant digits, respectively (e.g., if the results of the continuous laboratory test is <20 or <2.0, a value of 19.99 or 1.999, respectively, will be assigned in computing summary statistics; if the results of the continuous laboratory test is >20 or >2.0, a value of 20.01 or 2.001, respectively, will be assigned in computing summary statistics). Kidney injury molecule-1 (KIM-1) values that are reported as below the level of quantitation (<0.112) will deviate from the above rule and will be imputed as 0.099.

## 5.2.6 Handling of Incomplete Dates

An incomplete date will occur when the exact date an event occurred or ended cannot be obtained for a patient. Incomplete dates will be imputed as described below. No other imputation of missing data will be performed.

- For a partial or missing medication date, the medication will be classified as a concomitant medication unless the available part of the date indicates it is impossible for the drug to be concomitant. For example, if only the year for the stop date is available and the year is prior to the year of dosing, the medication will be classified as a prior medication.
- For a partial or missing AE onset date, the event will be classified as treatment emergent if the month and/or year of the onset date are on or after the initiation of eteplirsen and within 28 days of the last dose of eteplirsen. If a partial AE onset

Statistical Analysis Plan for Final Analysis

date is after the treatment end date, then the date will be imputed as the first day of the month.

• For the purpose of calculating the time since DMD diagnosis or duration of prior corticosteroid use, if the date of DMD diagnosis or the start date of corticosteroid use has a missing day but known month and year, then the 15th of the month will be used in the calculation. If the date has a missing day and month and only the year is known, December 31st of the recorded year will be used in the calculation.

In all cases, the original missing or incomplete dates will be presented in the data listings.

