## 5.7. Algorithm, Computation and Definition of Derived Variables

#### Day 1

Day 1 in Study 4658-102 will be defined as the date of the first eteplirsen administration in Study 4658-102.

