#### Time since DMD Diagnosis

The time since DMD diagnosis, in months, will be calculated as (Day 1 - Date of DMD diagnosis + 1)/30.4375.

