#### **Duration of Corticosteroid Treatment**

The duration of corticosteroid treatment, in months, will be calculated as (Day 1 - Date on which the patient started corticosteroid treatment + 1)/30.4375.

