## 6.2. Demographics and Baseline Characteristics

Demographic and Baseline characteristics will be summarized overall and by age cohort. These variables will include age (months), EudraCT age category, race, ethnicity, height/length (cm), weight (kg), BMI (kg/m^2), mutation, time from DMD diagnosis (months) to Baseline, corticosteroid medication type, corticosteroid frequency, duration of prior corticosteroid use at Baseline.

Patient-level demographic data and Baseline characteristics will be presented in data listings.

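### The 31 December rule for year-only diagnosis and corticosteroid-start dates can give negative baseline durations and never errs on the long side

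*SAP*

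**What the plan says.** SAP section 5.2.6 gives two rules for a DMD diagnosis date or a corticosteroid start date. If only the day is missing, "then the 15th of the month will be used in the calculation". The second rule covers a record that holds nothing but the year ("If the date has a missing day and month and only the year is known"), and for that case the SAP states that "December 31 st of the recorded year will be used in the calculation". The same section says "No other imputation of missing data will be performed", and it keeps the original partial dates in the listings.

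The dates feed two variables in SAP section 5.7, both in months. Time since diagnosis is "Day 1 - Date of DMD diagnosis + 1)/30.4375" and duration of corticosteroid treatment is "Day 1 - Date on which the patient started corticosteroid treatment + 1)/30.4375". The reference date is the first dose: "Day 1 in Study 4658-102 will be defined as the date of the first eteplirsen administration in Study 4658-102".

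SAP section 6.2 summarises both variables overall and by age cohort, the first as "time from DMD diagnosis (months) to Baseline". Under SAP section 5.1 a continuous variable is shown with its mean, SD, median, minimum and maximum.

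**The concern.** A missing day is placed in the middle of the month, but a missing day and month is placed at the very end of the year. That has two consequences.

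- **Impossible values.** If the recorded year is the year of the first dose, 31 December almost always falls after Day 1 and the duration becomes negative. Protocol section 8.2 requires an established clinical diagnosis at entry, so the diagnosis cannot come after the first dose. Day 1 is a known upper limit that the rule does not use. The medication bullet in the same SAP section does ask what the known part of a date makes impossible; the diagnosis and corticosteroid bullet does not.
- **Error in one direction.** 31 December is the latest date the year allows, so the rule can shorten a duration but never lengthen it.

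These variables describe how long the children had been diagnosed and on corticosteroids at entry. Patients are 6 to 48 months old and Cohort 2 is under 24 months, so an error of several months is large against any duration that is possible.

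**Working it through.** The documents state no figure on this point, so there is nothing to reproduce. The check applies the SAP's own formula to the imputed date.

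**Inputs.** The imputed date is 31 December of the recorded year (SAP 5.2.6). Duration = (Day 1 - date + 1)/30.4375 months (SAP 5.7). Each cohort has about 6 patients (SAP 4.1). Assumption, not in the documents: the true date is uniform over the days on which it could fall.

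**Recorded year is the year of Day 1**

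| Day 1 | Days from Day 1 to 31 December | Formula | Months |
|---|---|---|---|
| 31 March | 275 | (-275 + 1)/30.4375 | -9.00 |
| 30 June | 184 | (-184 + 1)/30.4375 | -6.01 |
| 30 September | 92 | (-92 + 1)/30.4375 | -2.99 |
| 29 December | 2 | (-2 + 1)/30.4375 | -0.03 |
| 30 December | 1 | (-1 + 1)/30.4375 | 0 |
| 31 December | 0 | (0 + 1)/30.4375 | 0.03 |

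The result is negative on every Day 1 from 1 January to 29 December, which is 363 of 365 days. The mean shortening, with the true date uniform from 1 January to Day 1 (2020 calendar), is:

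- Day 1 on 31 March: (275 + 365)/2 = 320 days, or 10.51 months.
- Day 1 on 30 June: (184 + 365)/2 = 274.5 days, or 9.02 months.
- Day 1 on 30 September: (92 + 365)/2 = 228.5 days, or 7.51 months.

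**Recorded year is earlier than the year of Day 1**

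The result is never negative. Shortening = (31 December - true date)/30.4375. In a 365-day year this runs from 0 to 364/30.4375 = 11.96 months, with mean 182/30.4375 = 5.98 and SD 3.46. Only about 17% of true dates give a shortening of 5 to 7 months.

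Example: with Day 1 on 30 June 2020 and recorded year 2019, the rule gives (182 + 1)/30.4375 = 6.01 months. The true value could be anything from 6.01 to (546 + 1)/30.4375 = 17.97.

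**Effect on a cohort summary**

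One earlier-year record among 6 patients lowers the cohort mean by 5.98/6 = 1.0 month on average and by at most 11.96/6 = 2.0. One same-year record with Day 1 on 31 March lowers it by 10.51/6 = 1.75 on average. If other values are valid, a single negative value becomes the minimum in the table.

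**How often a year-only record would be negative**

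This depends on how recent the event is. Suppose Day 1 is uniform over the year and the true time since the event is uniform on 0 to M years, with M at least 1 (both assumptions). The share of year-only records that turn negative is then about 1/(2M): 50% for M = 1, 25% for M = 2 and 17% for M = 3.

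**The mid-month rule**

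The 15th can also fall after Day 1 in the same month, but by little. With Day 1 on the 1st, the result is (-14 + 1)/30.4375 = -0.43 month.

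**The case against.** The strongest reply is that this may never happen. The documents do not say how many year-only dates exist. The children are very young, so a diagnosis is recent and its month is likely to be known. Protocol section 12 provides for full source data verification and queries on missing data. This stands: the effect is conditional and may be nil.

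The reach is also narrow. The two variables appear only in the baseline summary. The SAP plans no covariate adjustment (5.4) and no subgroups (5.5), and neither variable enters the safety or PK endpoints. A reader might infer that the trial's main results are affected; nothing in the documents supports that. Because the partial dates are listed, a reader could also trace an odd value among about 12 patients. That helps interpretation but does not correct the table.

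A reader might further infer that every year-only duration is cut by about 6 months. The documents do not support this. Six months is an average under a uniform assumption; a single earlier-year record can lose anything from nothing to 12 months, and a same-year record typically loses more than 6.

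For earlier years, one can say that 31 December is a deliberate lower-bound convention, since it yields the shortest duration the year allows. That is a fair description, but the SAP does not state it as the aim, and the rule for a missing day follows the opposite, mid-interval convention. The defence does not reach the same-year case, where the value is impossible for a diagnosis that preceded dosing.

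Finally, the text of SAP sections 5.2.1 to 5.2.4 is not shown, so a guard there cannot be ruled out. It is unlikely, because 5.2.6 is the section that governs dates.

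**Conclusion.** Wrong as written, with low impact. The year-only rule, applied through the SAP's own formulas, gives negative durations for same-year records on all but the last two days of the year. This follows from the text alone and needs no distributional assumption. For earlier years the rule always takes the latest possible date. The shortening is 0 to 12 months, and the average of about 6 rests on a true date uniform over the year.

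The consequence is confined to time since diagnosis and duration of prior corticosteroid use in the baseline table. It arises only if year-only dates occur, and their number is not given. With about 6 patients per cohort, one such record is enough to be visible in the mean and the minimum.

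**What to change.** Replace the year-only rule in SAP section 5.2.6: when only the year is known, impute the midpoint of the possible interval, from the later of 1 January of that year and the date of birth to the earlier of 31 December and Day 1. Add that a date imputed to the 15th is capped at Day 1. For corticosteroids, apply the Day 1 limit only where use is known to have begun before the first dose, because a same-year start could otherwise be later.

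The midpoint is never negative. For a same-year record it gives 1.51, 3.02 and 4.53 months for Day 1 on 31 March, 30 June and 30 September 2020, when birth falls before that year. A fixed 1 July would not do: without a cap, Day 1 on 31 March still gives -2.99 months. With a cap at Day 1, every same-year record with Day 1 on or before 1 July collapses to one day (0.03 month).

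The cost is two or three SAP sentences and a small change to the derivation. The SAP lists age in months and does not mention date of birth. If birth date is not held, the lower limit can be 1 January alone; that still prevents negative values but not a duration longer than the child's age. No new data collection is needed for the upper limit, and the partial dates stay in the listings as planned.

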#### 5.2.7 Imputation of Relationship or Severity for Adverse Events

In the summary of AEs, events with missing relationship or severity will be presented as "Related" or "Severe", respectively. However, missing values will be presented in the data listings as missing.

## 5.3. Multiple Testing and Comparisons

No adjustment will be made for the testing of multiple endpoints.

## 5.4. Adjustment for Covariates

Not applicable.

## 5.5. Subgroups

Due to small sample size, no subgroups will be identified for this study.

## 5.6. **Presentation Over Time**

For endpoints that are collected serially over time, assessments/test values will be assigned to a specific timepoint (e.g., study week) based upon the electronic case report form (eCRF) page on which the assessments/test values were reported.

For safety endpoints, unscheduled assessments will not be included in the summary by timepoint.

## 5.7. Algorithm, Computation and Definition of Derived Variables

#### Day 1

Day 1 in Study 4658-102 will be defined as the date of the first eteplirsen administration in Study 4658-102.

#### Study Day

Study day will be defined as Event Date – Day 1 + 1, if Event Date is on or after Day 1; otherwise, as Event Date – Day 1, if Event Date precedes Day 1. Study Day will be defined for Study 4658-102

#### **Duration on Study**

Duration on study will be calculated as the duration in weeks from Day 1 to the date of study completion/discontinuation as recorded on the END OF STUDY eCRF (if completed) or the date of the last study assessment or procedure plus 7 days. This calculation will be performed for each study.

#### **Duration on Eteplirsen**

Duration on eteplirsen will be calculated as the duration in weeks from Day 1 to the date of the last eteplirsen administration as recorded on the study drug administration eCRF plus 6 days (i.e., [last dose – first dose date  $\pm 7$ ]/7).

Duration in weeks calculated above will be then categorized to 1 of the following intervals for Study 4658-102: <24, 24 to <48, 48 to <72, 72 to < 96, and 96 weeks.

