- ^e Weight measured will be measured prior to study drug infusions at thespecified visits.
- f Height/length will be measured as part of every physical examination. The examination will include general appearance; head, ears, eyes, nose, throat; heart; lungs; chest; abdomen; skin; lymph nodes; musculoskeletal; and neurological systems.
- h A 2-week window is allowed in the event thechild is unable to complete this assessment at a given visit.
- Only performed in patients 36 months of age and older.
- Patients should receive eteplirsen once every 7 days relative to the Study Week 1 date. A window of ±3 days from the scheduled doseis acceptable after the first infusion. Patients may not receive 2 separate doses of eteplirsen within thesame 60-hour period. The Medical Monitor should be contacted in the event of ≥2 consecutive missed doses.
- ¹ Renal function blood tests includecreatinine, blood urea nitrogen, and serum cystatin C.
- m. Quantitative urine analysis includes KIM-1 and urinalysis (pH, specific gravity, protein, glucose, ketones, cytology, and hemoglobin).

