The dose-titration period will last 10 weeks overall (1 infusion/week) to slowly achieve the target dose of 30 mg/kg. Eteplirsen dosing will begin at 2 mg/kg for 2 weeks (Weeks 1 and 2) and will escalate to 4 mg/kg (Weeks 3 and 4), 10 mg/kg (Weeks 5 and 6), 20 mg/kg (Weeks 7 and 8), and 30 mg/kg (Weeks 9 and 10). Patients will continue to receive 30 mg/kg eteplirsen for the duration of the study. The duration of each patient's treatment in the study is expected to be at least 48 weeks (including the 10-week titration period), and patients may continue to receive treatment in the study for up to 96 weeks determined by the Investigator based on the absence of any safety signal and an indication of clinical benefit.

In addition, study drug may be interrupted or discontinued for specific safety reasons.

Safety will be regularly assessed throughout the study via the collection of AEs, clinical safety laboratory tests (blood chemistry, hematology, renal function, coagulation, and urinalysis), electrocardiograms (ECGs), echocardiograms (ECHOs), vital signs, and physical examinations.

Plasma and urine samples for PK assessments will be collected at Week 2 (2-mg/kg dose level), Week 6 (10-mg/kg dose level), Week 8 (20-mg/kg dose level), and at Weeks 10 and 24 (30-mg/kg dose level). Serial PK samples will be collected pre-dose, immediately prior to the end of infusion (prior to flush), and approximately 1-3 hours and 6-8 hours after completion of study drug infusion. Urine PK samples will be collected over the first 4 hours after start of infusion.

Approximately 4 weeks after the last eteplirsen infusion (regardless of the duration of the patient's participation in the study), patients will be required to return to the study site for safety evaluations. The total duration of patient participation, including Screening, Titration/Treatment, and Safety Follow-up periods is up to 101 weeks.

Refer to Section 10 for the detailed list of study assessments.

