9.2. Treatments Administered

Eligible patients will receive a once weekly IV infusion of eteplirsen for up to 96 weeks. Eteplirsen should be prepared for dosing by following the steps detailed in the study-specific Pharmacy Manual.

The starting dose is 2 mg/kg eteplirsen, with escalation to 4, 10, 20, and 30 mg/kg over the course of the dose-titration period.

The following guidelines for the timing of dosing should be followed throughout the study:

- Patients should receive Eteplirsen once every 7 days starting on Week 1. A window of ± 3 days from the scheduled dose is acceptable after the first infusion.
- Patients may not receive 2 separate doses of Eteplirsen within the same 60-hour period.
- The Medical Monitor should be contacted in the event of ≥2 consecutive missed doses.

The administered dose is calculated by patient weight, which will be collected on a weekly basis and used to calculate the dose to be administered at the next visit(s). For example, the weight collected at Week 2 will be used to calculate the doses to be infused during the Week 3 visit.

Eteplirsen should be diluted in a normal saline, where the final volume, after eteplirsen has been added, equals the volume appropriate for the patient's weight. The drug delivery bag, syringe or flask is to be labeled in accordance with standard pharmacy practice and to include total volume as well as drug dose in milligrams. Eteplirsen will be diluted in normal saline to a total volume per Table 5 and infused IV for approximately 35 to 60 minutes using an infusion or syringe

pump. It is recommended that a topical anesthetic cream be applied to the infusion site prior to each administration of eteplirsen.

Table 5: Example Eteplirsen Dilution Scheme

Patient Weight	Total Eteplirsen Dose (30 mg/kg)	Total Volume of Eteplirsen Drug Product	Dilution in Saline up to Total Volume of:	Maximum Eteplirsen Concentration in Infusion
<5 kg	<150 mg	<3 mL	10 mL	15 mg/mL
5 to 10 kg	150 to 300 mg	3 to 6 mL	15 mL	20 mg/mL
10 to 15 kg	300 to 450 mg	6 to 9 mL	25 mL	18 mg/mL
15 to 25 kg	450 to 750 mg	9 to 15 mL	50 mL	15 mg/mL
>25 kg	>750 mg	>15 mL	100 mL	

Note: Refer to the Pharmacy Manual for other dosing dilution schemes.

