#### Patient Years on Eteplirsen

The patient years on eteplirsen will be calculated as (Last Treatment Date - First Treatment Date + 7)/365.25.

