## 6.7. Exposure to Study Drug

The exposure to eteplirsen will be summarized for eteplirsen-treated patients in the Safety Analysis Set. The variables will include the following (as applicable): total number of infusions received, total number of infusions on 30 mg/kg of eteplirsen received, cumulative amount of drug received (mg), duration on eteplirsen in 24-week intervals, and patient years on eteplirsen. For both the 4658-102 final analyses, these endpoints will be calculated cumulatively

Patient-level study drug information will be provided in a data listing. Additionally, a listing of the derived exposure parameters above will be generated as well as a listing of overdoses. The actual dose will be compared to the planned dose. Any actual dose that is greater than 1.10 times of the planned dose will be considered an overdose. Planned dose is calculated as the dose level in mg/kg multiplied by the patient's most recent weight prior to the dose (or on the same day with no time).

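### The exposure-duration categories cut exactly at 48 and 96 weeks with no allowance for the ±3-day dosing window, so a full course ending 1 to 3 days early is tabulated one category lower

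*SAP*

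**What the plan says.** SAP 5.7 (Duration on Eteplirsen) counts the weeks from Day 1 to the date of the "last eteplirsen administration as recorded on the study drug administration eCRF plus 6 days". It then assigns the result to one of five categories: "<24, 24 to <48, 48 to <72, 72 to < 96, and 96 weeks". No tolerance is stated. SAP 6.7 puts "duration on eteplirsen in 24-week intervals" in the exposure summary, beside the total number of infusions, infusions at 30 mg/kg, cumulative amount and patient-years. It also calls for patient-level dosing data and a listing of the derived exposure parameters.

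The dosing calendar is in the protocol. A footnote to Table 3 says "Patients should receive eteplirsen once every 7 days relative to the Study Week 1 date", so a shifted dose does not move the later ones. Protocol 9.2 adds "A window of ± 3 days from the scheduled dose is acceptable after the first infusion" and "Patients may not receive 2 separate doses of Eteplirsen within the same 60-hour period". Protocol 7.1 plans a minimum of 48 weeks of treatment, titration included, and allows continuation to a maximum of 96.

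**The concern.** The two planned course lengths are 48 and 96 weeks, and the category boundaries stand at the same two values. A child on the exact schedule therefore sits on the boundary, and an early last appointment that the protocol accepts moves that child down a category.

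Protocol 5.4 states the purpose as safety over at least 48 and up to 96 weeks of dosing, in an age group not studied before. Protocol 5.3 and 7.2 describe programme exposure as numbers treated for at least 48 and at least 96 weeks, so readers are likely to look for the same counts here. With about 12 children, in cohorts of about 6, one child is 1/12 = 8% of the total or 1/6 = 17% of a cohort. Those counts should not depend on the weekday of the last visit.

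**Working it through.** **Inputs**

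- Duration formula (SAP 5.7): (last dose − first dose + 7)/7 weeks. The available text prints ± before the 7; I read it as +. Adding 6 days and counting inclusively gives +7, and the patient-years formula in the same section, "Last Treatment Date - First Treatment Date + 7)/365.25", uses +7 with the same two dates.
- Interval (Protocol Table 3 footnote): 7 days, anchored to the Week 1 date.
- Window (Protocol 9.2): ±3 days after the first infusion.
- Minimum spacing (Protocol 9.2): 60 hours. A last dose 3 days early after an on-time dose leaves 7 − 3 = 4 days = 96 hours, so it is allowed.

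**Formula.** If treatment ends with the n-th scheduled infusion, given s days off schedule, last − first = 7(n − 1) + s, so duration = n + s/7 weeks.

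**On schedule (s = 0).** n = 48: (329 + 7)/7 = 48.000. n = 96: (665 + 7)/7 = 96.000. Both planned lengths are reproduced, and both equal a cut point. This also supports the +7 reading: +6 would give 47.857 and 95.857, and −7 would give 46.0 and 94.0.

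**Last dose early**

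| Days early | 48 infusions (weeks) | Category | 96 infusions (weeks) | Category |
|---|---|---|---|---|
| 0 | 48.000 | 48 to <72 | 96.000 | 96 |
| 1 | 47.857 | 24 to <48 | 95.857 | 72 to <96 |
| 2 | 47.714 | 24 to <48 | 95.714 | 72 to <96 |
| 3 | 47.571 | 24 to <48 | 95.571 | 72 to <96 |

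Under +6 or −7 the early children are also in the lower category, so the result does not depend on the damaged sign.

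**Is there a 96th infusion at Week 96?** The dosing row of Table 3 is blank in the available text. The stated total participation of up to 101 weeks equals 2 (screening) + 95 (first to 96th infusion) + 4 (follow-up). With 96 weeks between first and last infusion it would be 2 + 96 + 4 = 102. The total therefore fits a 96th infusion 95 weeks after the first. If the last planned infusion were instead at Week 95, even an on-schedule child would have 95.0 weeks and miss the top category.

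**Share affected.** The documents give no distribution of visit days. If all seven allowed days were equally likely (assumption), 3/7 = 43% of last doses would be early, and 0.43 × 12 = 5.1 children. If 10% were early (assumption), 0.10 × 12 = 1.2 children. Both figures need all 12 to end exactly at the 48th or 96th infusion.

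**Check of cuts at 47.5 and 95.5.** The latest 47th infusion gives 47 + 3/7 = 47.429 and the earliest 48th gives 48 − 3/7 = 47.571. The latest 95th gives 95.429 and the earliest 96th gives 95.571. Each cut lies between its pair, so it separates the courses over the whole window.

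**The case against.** The variable is elapsed time on drug from actual dates, and 95.57 weeks is less than 96. The SAP nowhere says a category means that the full course was received, so the tabulation is literally true. SAP 6.7 also reports infusion counts and lists the derived parameters, so with about 12 children each child's course can be read directly. These points stand, and they limit this to a matter of presentation. They do not remove it: the formula makes an uninterrupted weekly course equal its nominal number of weeks, so equal courses are split at the cut by the appointment day alone.

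A reader might infer more than the documents support:

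- *That about 5 of 12 children will be misplaced.* This needs every child to end exactly at infusion 48 or 96 and the last dose to be spread evenly over the window. Nothing in the documents supports an even spread, since the window is a tolerance around a fixed day. A child who continues past the 48th infusion is not affected at that cut.
- *That a last dose 1 to 3 days late (96.14 to 96.43 weeks) fits no category.* This follows only if the bare 96 is literal. A sign was evidently damaged in the same section, so a lost ≥ is the likelier explanation.
- *That the trial's main exposure claim, or its completer count, is wrong.* No section gives these categories that standing. Protocol 8.4 defines completers by the Week 48 assessments, and SAP 6.1 summarises completion through Week 96. Neither uses drug duration, and the two quantities can differ legitimately.

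**Conclusion.** The point holds as a minor one. A child with every infusion and the last one 1 to 3 days early, inside the accepted window, is tabulated one category below a child with the same infusions on schedule. At the 48-week cut this applies only to children whose treatment ends with the 48th infusion.

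The number affected is unknown. About 1 to 5 of 12 is a conditional range, and its upper end is close to the worst case. The conclusion rests on reading the formula as +7, although the early-side result survives the other readings, and at the upper cut on a 96th infusion at Week 96, which is inferred. One descriptive table is affected. Infusion counts and listings stay correct, and no safety conclusion changes.

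**What to change.** First confirm that the last planned infusion is at Week 96; if it is not, the upper cut must be set to match. Then, in SAP 5.7, lower the 48- and 96-week cuts to 47.5 and 95.5 weeks, write the top category with ≥, and footnote that the labels are nominal weeks allowing for the ±3-day window. Moving the 24- and 72-week cuts to 23.5 and 71.5 is optional and for consistency only, because no planned course ends there.

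The cost is one line of SAP text and a footnote, with no new data and no change in conduct. The small downside is that a duration of 95.57 weeks appears under a nominal 96-week label, which the footnote discloses.
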